1.2 STUDY DESIGN

This is a Phase II, randomized, multi-center, multinational, open-label, cross-over study in adult participants with PD-L1–positive NSCLC.

The study will evaluate participant- and HCP-reported preference for atezolizumab SC compared with atezolizumab IV.

Figure 1 Study Schema

eNSCLC=early non-small cell lung cancer; IV=intravenous; PD-L1=programmed death-ligand 1; Q3W=every 3 weeks; R=randomization; SC=subcutaneous; TC=tumor cells; TPS=tumor proportion score.

- (1) Histological or cytological diagnosis per UICC/AJCC staging system, 8th Ed.
- (2) PD-L1 positive defined as minimum TC $\geq 1\%$ by VENTANA PD-L1 (SP263) IHC assay or TPS $\geq 1\%$ by Dako PD-L1 IHC 22C3 pharmDx assay performed by a local or central laboratory.
- (3) PD-L1 high defined as minimum TC $\geq 50\%$ by VENTANA PD-L1 (SP263) IHC assay, minimum TPS $\geq 50\%$ by Dako PD-L1 IHC 22C3 pharmDx assay, or TC3 or IC3 by VENTANA PD-L1 (SP142) IHC assay, performed by a local or central laboratory.
- (4) Stratification: disease stage and type of surgery.

Two populations will be included: participants with resected Stage II, IIIA and selected IIIB (T3-N2) NSCLC who have completed adjuvant platinum-based chemotherapy without evidence of disease relapse/recurrence, and chemotherapy-naive participants with Stage IV NSCLC.

Participants whose tumors have an EGFR mutation or ALK rearrangement will be excluded from enrolment. Participants with tumors of non-squamous histology with unknown EGFR or ALK mutational status will be required to be tested at prescreening/screening centrally if the local test cannot be done or does not meet the required criteria.

Eligibility will be assessed within a 28-day screening period. A pre-screening period will be available for those participants who need to assess their eligibility in terms of PD-L1 expression, EGFR mutation, or ALK rearrangement.

Participants who do not meet the criteria for participation in this study (screen failure) may qualify for two re-screening opportunities (for a total of three screenings per participant) at the investigator's discretion, provided all initial and subsequent screening assessments are performed within 56 days prior to Day 1. Re-screened participants must meet all eligibility criteria and re-sign the Informed Consent Form prior to re-screening. The investigator will record reasons for screen failure.

Participants must have PD-L1-positive or high NSCLC to be enrolled in the study. Participants that do not have prior PD-L1 testing will be prospectively tested for PD-L1 expression by central testing at prescreening/screening.

Participants will undergo a tumor assessment at baseline to confirm eligibility criteria. Subsequent tumor assessments will be conducted as per local standard of care.

Participants with Early-Stage NSCLC

Eligible participants with early-stage NSCLC will have had a complete resection of NSCLC and must be adequately recovered from surgery and adjuvant chemotherapy. Prior to treatment with adjuvant atezolizumab, all participants should have received up to four cycles of adjuvant platinum-based chemotherapy, with no evidence of disease relapse/recurrence.

Chemotherapy-Naive Participants with Stage IV NSCLC

Participants with Stage IV NSCLC will be eligible to join the study if they have not received prior chemotherapy for advanced NSCLC and satisfy the eligibility criteria described.

1.2.1 Treatment Assignment

This is a randomized, open-label study. After written informed consent has been obtained, all screening procedures and assessments have been completed, and eligibility has been established for a participant, the study site will obtain the participant's identification number and treatment assignment from the interactive voice or web-based response system (IxRS).

Participants will be randomly assigned to one of two treatment arms: Arm A (atezolizumab SC followed by atezolizumab IV) or Arm B (atezolizumab IV followed by atezolizumab SC). Randomization will occur in a 1:1 ratio through use of a permuted-block randomization method to ensure a balanced assignment to each treatment arm. Randomization will be stratified by disease stage (II, III, IV) and type of surgery (no surgery, pneumonectomy, any other lung surgery).

1.2.2 Independent Review Facility

No Independent Review Facility (IRF) will be used for this study.

1.2.3 Data Monitoring

No data monitoring will be conducted for this study.

2. STATISTICAL HYPOTHESES AND SAMPLE SIZE DETERMINATION

2.1 STATISTICAL HYPOTHESES

The primary objective for this study is to evaluate participant- and HCP-reported preference for atezolizumab SC compared with atezolizumab IV.

There will be no formal hypothesis test for the primary endpoint.

2.2 SAMPLE SIZE DETERMINATION

The planned total sample size of 175 participants is based on an assumed rate of 70% of participants preferring atezolizumab SC compared with atezolizumab IV. To achieve a distance of approximately $\pm 8\%$ from the estimated proportion to 95% CI limits, a total of 126 participants are needed for the evaluation of preference. The final target sample size will be increased to approximately 175 participants to allow for 28% of the participants not providing an evaluable preference assessment.

Approximately 175 participants from approximately 40–50 study sites worldwide will be randomized in the study. Up to one-third of the study population will comprise chemotherapy-naive participants with Stage IV NSCLC; this proportion may be increased if sufficient participants with early-stage NSCLC are not recruited. Participants who withdraw from the study following randomization will not be replaced.

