6. STATISTICAL CONSIDERATIONS AND ANALYSIS PLAN

The primary study analysis will take place when all study participants have completed their last study treatment administration in the Treatment Cross-over Period. Summaries of secondary study endpoints, including PK and ADA measurements, participant-reported TASQ and EORTC QLQ-C30 responses, selection of treatment administration method for the Treatment Continuation Period, HCP reported HCPQ responses, and safety endpoints, up to Day 1, Cycle 7 will be included in the primary analysis.

The final study analysis that includes all secondary endpoints including all questionnaires, PK, ADA, and safety endpoints will be conducted after the end of the study (i.e., when all patients have received 16 cycles of atezolizumab or discontinued study treatment).

For the definition of study populations, please refer to the Statistical Analysis Plan (SAP). The definitions of primary and secondary objectives and the corresponding estimand definitions and further details about the planned analyses will be presented in the SAP.

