6.1 DETERMINATION OF SAMPLE SIZE

The primary study objective is to estimate the proportion of participants who express a preference for atezolizumab SC compared with atezolizumab IV.

The planned total sample size of 175 participants is based on an assumed rate of 70% of participants preferring atezolizumab SC compared with atezolizumab IV. To achieve a distance of approximately $\pm 8\%$ from the estimated proportion to 95% CI limits, a total of 126 participants are needed for the evaluation of preference. The final target sample size was increased to approximately 175 participants to allow for 28% of the participants not providing an evaluable preference assessment.

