4.2.2 Main Analytical Approach for Primary Estimand

Patient preference will be summarized and presented by overall and by randomized treatment sequence using FAS. As stated in [Table 1](#), for intercurrent events such as patients who died, early discontinued from treatment or never received any study treatment, as well as patients lost to follow-up prior to providing an answer to Question 1 of the PPQ will be excluded from the analysis. Responses to Question 1 of the PPQ collected before at least two consecutive administrations of treatment, with each treatment administration route, were received by the patient will not be included in the analysis.

Patient preference will be summarized by presenting the number and proportion of patients in each category (SC, IV and No preference). A point estimate with associated exact Clopper-Pearson binomial 95% CI for the proportion of patients who preferred atezolizumab SC will be calculated and will be displayed by randomized treatment sequence and overall.

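### Does the stated precision of about ±8 points at 126 evaluable participants conflict with the Clopper-Pearson interval the SAP will report?

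*SAP*

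**What the plan says.** SAP 2.2 states that the planned total of 175 "is based on an assumed rate of 70% of participants preferring atezolizumab SC compared with atezolizumab IV". The target is a distance of approximately 8 points either way "from the estimated proportion to 95% CI limits, a total of 126 participants are needed for the evaluation of preference". The 126 is then raised to about 175 to allow for 28% without an evaluable preference answer. Protocol 6.1 gives the same reasoning and the same figure ("a total of 126 participants are needed for the evaluation of preference"). Neither section names the type of interval used for sizing.

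The analysis method appears only in SAP 4.2.2: "A point estimate with associated exact Clopper-Pearson binomial 95% CI for the proportion of patients who preferred atezolizumab SC will be calculated". Protocol 6.4 promises a point estimate and a 95% CI without naming a method, and Protocol section 6 says that "further details about the planned analyses will be presented in the SAP".

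On inference, SAP 2.1 is explicit: "There will be no formal hypothesis test for the primary endpoint".

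**The concern.** With no test and no power calculation, the width of the interval is the only stated justification for the sample size. A reader is entitled to expect that the quoted precision describes the interval that will be reported. The quoted figure is symmetric and matches a Wald interval, while the planned interval is exact, wider and asymmetric. If the difference were large, the study would be less precise than claimed, and on the lower side, which readers use to judge how firmly a majority preference is supported. A reader given 70% ± 8 would expect a lower limit of 62%.

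**Working it through.** **Inputs.** Assumed preference p = 0.70, evaluable n = 126, target distance d = 0.08, 95% two-sided interval and 28% non-evaluable, all from SAP 2.2 (Protocol 6.1 agrees). The analysis interval is Clopper-Pearson, from SAP 4.2.2. z = 1.96.

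**1. Reproduce the plan's figures.** The Wald formula gives

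n = z² p(1 − p) / d² = 3.8415 × 0.21 / 0.0064 = 126.05.

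The half-width at 126 is 1.96 × √(0.21/126) = 0.0800, so 8.00 points (62.0% to 78.0%). The inflation is 126 / (1 − 0.28) = 175.0. Both numbers reproduce. Other formulas at n = 126 and 70% do not give 8.00: Wald with continuity correction gives 8.40, Wilson a half-width of 7.9 and Clopper-Pearson 8.3. The Wald origin is therefore a strong inference, but the documents do not state it.

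**2. Clopper-Pearson at the same inputs.** For x responders out of n, the lower limit is the 2.5% quantile of Beta(x, n − x + 1) and the upper limit is the 97.5% quantile of Beta(x + 1, n − x).

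| Case, n = 126 | Limits | Below | Above | Half-width |
|---|---|---|---|---|
| 88/126 (69.8%) | 61.0% to 77.7% | 8.8 | 7.9 | 8.3 |
| 89/126 (70.6%) | 61.9% to 78.4% | 8.8 | 7.8 | 8.3 |
| Mean over Binomial(126, 0.70) | 61.2% to 77.8% | 8.77 | 7.80 | 8.28 |

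Against a stated 8, the mean half-width is 0.28 point over, the upper distance is 0.20 under and the lower distance is 0.77 over.

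**3. How often each measure stays near 8.** With 126 evaluable and a true rate of 70%:

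| Measure | Probability ≤ 8.0 | Probability < 8.5 (rounds to 8 or less) |
|---|---|---|
| Half-width | 15% | 77% |
| Lower distance | 0.4% | 11% |

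**4. Compare with the plan's own assumptions.** Keep n = 126, average over the binomial and vary the true rate:

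| True rate | Below | Above | Half-width |
|---|---|---|---|
| 65% | 8.97 | 8.24 | 8.60 |
| 70% | 8.77 | 7.80 | 8.28 |
| 75% | 8.46 | 7.24 | 7.85 |
| 80% | 8.01 | 6.55 | 7.28 |

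Relative to 70%, the half-width moves by 8.60 − 8.28 = 0.32 at 65%, by 8.28 − 7.85 = 0.43 at 75% and by 8.28 − 7.28 = 1.00 at 80%. Each shift is larger than the 0.28-point effect of the interval method.

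Now vary the number evaluable. These figures are evaluated at exactly 70%, interpolating where 0.7n is not a whole number, so they are a separate series from the table above. With 120 evaluable (55/175 = 31% loss) the distances are 9.04 below and 8.02 above. With 137 (38/175 = 22% loss) they are 8.41 and 7.53.

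**5. What exact compliance would cost.** At 70%, holding the Clopper-Pearson half-width to 8.0 needs 137 evaluable, or 137/0.72 = 190.3, so 191 randomised. Holding the lower distance to 8.0 needs 151 evaluable, or 151/0.72 = 209.7, so 210 randomised. That is 16 or 35 more participants than 175, to bring the half-width down by about 0.3 point or the lower distance by about 0.8.

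**The case for a change.** The best argument for an edit is that SAP 2.2 speaks of the distance to the limits with a ± sign, which reads as a statement about each side. On the lower side it does not hold: the expected distance is 8.8, and at a true rate of 70% it is 8.5 or more about 89% of the time. Since precision is the sole basis for the sample size, one sentence giving the expected exact limits would cost almost nothing and would let any reader reproduce both figures.

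The arithmetic stands, and such a sentence would be accurate. But the plan says approximately, and the natural reading of a symmetric ± is the half-width, which rounds to 8. Nothing in either document says that the 8 points were a Clopper-Pearson distance, so no two statements conflict. Sizing by a closed-form approximation and analysing by an exact method is ordinary practice. A sentence recording the Wald origin would need the sponsor's confirmation, because that origin is only inferred. Rewording the SAP alone would also leave it quoting a different precision from Protocol 6.1 for the same 126 participants, a mismatch that does not exist today.

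**Conclusion.** No change follows. The plan leaves its sizing formula unnamed. The figure matches the Wald half-width of 8.00 points, and the prespecified Clopper-Pearson interval is expected to run from 61.2% to 77.8% (−8.8/+7.8, half-width 8.3). The shortfall is about 0.8 point on one side, in a figure labelled approximate, and is of the same order as the movement produced by modest errors in the assumed 70% or the assumed 28% loss.

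Nothing depends on it. There is no test and no threshold; 126, 175 and the choice of interval all stay as they are; and the report will give the exact limits at the number actually evaluable, so no reader will be misled about the precision achieved. If the sponsor later confirms the formula and is revising both documents for other reasons, adding the expected exact limits to SAP 2.2 and Protocol 6.1 together would be harmless but optional.

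This rests on 126 evaluable participants and a true preference rate of 70%. Across rates of 65% to 80% at 126 evaluable, and across 120 to 137 evaluable at 70%, the lower distance stays between 8.0 and 9.0 points, so the conclusion is not sensitive to either assumption.

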3. ANALYSIS SETS

The participant analysis sets for the purposes of analyses are defined in [Table 3](#).

Table 3 Participant Analysis Sets

Participant Analysis Set	Definition
Full Analysis Set (FAS)	All randomized participants.
Safety-Evaluable	All participants who received at least one dose of study treatment.
PK-Evaluable	All participants who received at least one dose of study treatment and had at least one post-baseline quantifiable PK sample available.
ADA-Evaluable	All randomized patients who have received at least one dose of study treatment and have at least one post-treatment ADA result.

ADA = anti-drug antibody; IxRS = interactive voice or web-based response system; PK = pharmacokinetic.

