6.7 IMMUNOGENICITY ANALYSES

The immunogenicity analysis population will consist of all participants with at least one ADA assessment. Participants will be grouped according to treatment received or, if no treatment is received prior to study discontinuation, according to treatment assigned.

The numbers and proportions of ADA-positive participants and ADA-negative participants at baseline (baseline prevalence) and after drug administration (postbaseline incidence) will be summarized by treatment group. When determining postbaseline incidence, participants are considered to be ADA positive if they are ADA negative or have missing data at baseline but develop an ADA response following study drug exposure (treatment-induced ADA response), or if they are ADA positive at

baseline and the titer of one or more postbaseline samples is at least 0.60 titer unit greater than the titer of the baseline sample (treatment-enhanced ADA response). Participants are considered to be ADA negative if they are ADA negative or have missing data at baseline and all postbaseline samples are negative, or if they are ADA positive at baseline but do not have any postbaseline samples with a titer that is at least 0.60 titer unit greater than the titer of the baseline sample (treatment unaffected).

The relationship between ADA status and safety and PK endpoints may be analyzed and reported via descriptive statistics.

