
 • Evaluate the immune response to atezolizumab 	
 • Prevalence of anti-drug antibodies (ADAs) to atezolizumab at baseline and incidence of ADAs to atezolizumab after initiation of study treatment • Evaluation of safety and PK by ADA status
Health Status Utility Objective	Corresponding Endpoint

 • Evaluate health status utility scores of participants treated with atezolizumab SC compared with atezolizumab IV 	
 • Change from baseline over time in EuroQoL EQ-5D-5L index-based and visual analogue scale (VAS) scores

[figure not shown]
ADA=anti-drug antibody; ECG=electrocardiogram; HRQoL=health-related quality of life; IV=intravenous; NCI CTCAE=National Cancer Institute Common Terminology Criteria for Adverse Events; SC=subcutaneous; TASQ=Therapy Administration Satisfaction Questionnaire.

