4. STATISTICAL ANALYSES

The analyses described in this SAP will supersede those specified in the Protocol Version 3, 7 March 2023 or thereafter.

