4.4.4 Exploratory Immunogenicity Analyses

The immunogenicity analyses will be based on the ADA-evaluable population.

Participants will be grouped according to treatment received or, if no treatment is received prior to study discontinuation, according to treatment assigned.

The numbers and proportions of ADA-positive participants and ADA-negative participants at baseline (baseline prevalence) and after drug administration (post-baseline incidence) will be summarized by treatment group. When determining post-baseline incidence, participants are considered to be ADA positive if they are ADA negative or have missing data at baseline but develop an ADA response following study drug exposure (treatment-induced ADA response), or if they are ADA positive at baseline and the titer of one or more post-baseline samples is at least 0.60 titer unit greater than the titer of the baseline sample (treatment-enhanced ADA response).

Participants are considered to be ADA negative if they are ADA negative or have missing data at baseline and all post-baseline samples are negative, or if they are ADA positive at baseline but do not have any post-baseline samples with a titer that is at least 0.60 titer unit greater than the titer of the baseline sample (treatment unaffected).

Descriptive analysis of safety and PK may be analyzed by ADA status.

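### Baseline ADA prevalence is computed in a set that requires a post-treatment ADA result but no baseline result, and its denominator is not stated

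*SAP*

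**What the plan says.** SAP Section 3, Table 3, defines the ADA-Evaluable set as "All randomized patients who have received at least one dose of study treatment and have at least one post-treatment ADA result". A baseline result is not required.

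SAP Section 4.4.4 applies this one set throughout: "The immunogenicity analyses will be based on the ADA-evaluable population". The summaries planned in it cover both time points: "The numbers and proportions of ADA-positive participants and ADA-negative participants at baseline (baseline prevalence) and after drug administration (post-baseline incidence"). No separate set or denominator is given for the baseline part. The same section expects some members to have no baseline result and classifies them for incidence only: "participants are considered to be ADA positive if they are ADA negative or have missing data at baseline but develop an ADA response".

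Baseline prevalence is a listed exploratory endpoint in SAP Section 1.1, Table 2: "Prevalence of anti-drug antibodies (ADAs) to atezolizumab at baseline and incidence of ADAs to atezolizumab after initiation of study treatment".

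Protocol Section 6.7 has a wider population: "The immunogenicity analysis population will consist of all participants with at least one ADA assessment". The SAP states that it governs: "The analyses described in this SAP will supersede those specified in the Protocol Version 3, 7 March 2023 or thereafter".

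**The concern.** Prevalence at baseline is fixed by the Cycle 1 pre-dose sample, so whether a participant counts should depend on having that result. Under Table 3 it depends on a later sample instead. Participants whose baseline status is known can be dropped, while participants whose baseline status is unknown are kept.

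Two consequences follow. First, known baseline results are discarded, and the reported prevalence is conditional on remaining in the study long enough to give a later sample. Second, because no denominator is stated, two programmers could follow the SAP and report different percentages, one over all set members and one over members with a baseline result.

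Section 4.4.4 also keeps the protocol's rule for grouping participants who were never treated. Nobody in a set that requires a dose can meet that condition, which suggests that the text was carried over from the wider protocol population without being refitted.

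**Working it through.** The documents state no ADA prevalence, no ADA-evaluable N and no count of missing ADA samples, so there is no figure of the plan's own to reproduce. The check is set logic first, then illustrations of size on labelled assumptions.

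**Step 1: who is in the set** (treated participants, SAP Table 3)

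| Baseline ADA result | Post-treatment ADA result | In the ADA-Evaluable set? | Baseline status known? |
|---|---|---|---|
| yes | yes | yes | yes |
| yes | no | no | yes |
| no | yes | yes | no |
| no | no | no | no |

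The second and third rows are the mismatch. For prevalence, the second should be in and the third should not count.

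**Step 2: dilution alone.** Assume N = 175 treated (the planned sample size, SAP Section 2.2), b participants with a baseline sample only, m with post-dose samples only, and the same true prevalence p in every group.

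- Set size = (175 − b − m) + m = 175 − b.
- Members with a baseline result = 175 − b − m.
- Percentage over all members = p × (175 − b − m)/(175 − b).
- Percentage over members with a baseline result = p.

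Results over all members:

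- b = m = 2, p = 5%: 5% × 171/173 = 4.9%.
- b = m = 9: the ratio is 157/166 = 0.946, so 2% reads 1.9%, 5% reads 4.7% and 10% reads 9.5%.
- b = 9, m = 18: the ratio is 148/166 = 0.892, so 5% reads 4.5% and 10% reads 8.9%.

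Across these inputs the relative lowering is about 1% to 11%. In absolute terms it is a few tenths of a point in most cases and 1.1 points at the extreme (10% prevalence with 18 missing baselines).

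**Step 3: exclusion and dilution together.** Assume 170 participants have a baseline result, 10 of them positive: 10/170 = 5.9%. Of the 170, 8 have no later sample; 5 others have a later sample but no baseline. The SAP set is then 170 − 8 + 5 = 167, of whom 162 have a baseline result. Let k be the number of positives among the 8 excluded.

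- Over all 167 members, (10 − k)/167 gives 6.0%, 5.4%, 4.8% and 4.2% for k = 0, 1, 2 and 3.
- If exclusion is unrelated to ADA status, the expected k is 8 × 10/170 = 0.47. The expected figure is 9.53/167 = 5.7%, which is 0.2 points below 5.9%.
- Over the 162 with a baseline result it is 9.53/162 = 5.9%, so no bias is expected.
- Under the same condition the chance of k ≥ 3 (hypergeometric: 170 participants, 10 positive, 8 drawn) is about 0.7%. The value 4.2% needs 3/8 = 37.5% positive among those excluded against 7/162 = 4.3% among those kept, and nothing in the documents points to such a difference.

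**The case against.** Several points on the other side carry weight.

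- *The denominator.* A participant with no baseline result is neither ADA positive nor ADA negative at baseline. The natural reading of Section 4.4.4 is therefore a proportion among those with a result, and then nothing is diluted. A reader might infer that every missing baseline sample lowers the reported prevalence. The SAP does not say that, and in the second illustration with k = 0 the figure is 6.0% against 5.9% despite five missing baselines. What stands is that the denominator is unstated. The general rule for categorical variables in SAP Section 4.1 does not settle it, although the SAP does state the base for the TASQ, continuation choice and HCPQ summaries.
- *Few should be excluded.* Protocol Appendix 2 schedules ADA samples before dosing at Cycles 2–6, 8 and 16 and at the treatment discontinuation visit. A treated participant must miss all of these to be baseline-only. This stands, and it is why the effect is small.
- *The narrowing is authorised.* Protocol Section 6 leaves population definitions to the SAP, and the SAP says that it supersedes. A reader might see a conflict between the documents, or conclude that the SAP created the missing-baseline question. Neither is supported: the protocol's population also admits participants with post-dose samples only. What the SAP set adds is the loss of baseline-only participants.
- *One common set is defensible.* Baseline status and incidence in the same people can be read together, and the treatment-enhanced category depends on the baseline titer. That is a reason to keep the set for incidence. It does not require discarding known baseline results from prevalence.
- *The leftover grouping clause.* It affects no participant and no number in the present set. It is purely editorial.

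**Conclusion.** The point holds in a limited form. By a stated rule, treated participants with a valid baseline ADA result and no later sample are left out of baseline prevalence for a post-baseline reason, and no other section of the SAP repairs this. The possible counting of members with no baseline result is an ambiguity, not a stated rule.

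The expected size is tenths of a percentage point under plausible missingness. This rests on assumed counts and assumed prevalences of 2% to 10%, and on exclusion being unrelated to ADA status. Figures as low as 4.2% against 5.9% should not be read as likely. Post-baseline incidence is unaffected, the endpoint is exploratory and descriptive, and no test, sample size or primary result depends on it. It is worth correcting because the right base is available from data already collected, but it is a minor improvement.

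**What to change.** In SAP Section 4.4.4:

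1. Compute baseline prevalence among participants with a non-missing baseline ADA result.
2. Keep the current ADA-Evaluable set for post-baseline incidence.
3. Report both Ns in the table.
4. Say whether the prevalence base includes untreated participants who have a baseline result. If it does, keep the untreated-participant grouping clause for prevalence; if not, delete the clause as an editorial clean-up.

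The cost is a few lines of SAP wording, with a matching entry or note in Table 3, and a second N in one table. No new data are needed.
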